7. RESEARCH QUESTION AND OBJECTIVES

The overall objective of this study is to evaluate characteristics, vaccine utilization and outcomes among vaccinated subjects with IC conditions. The primary analysis will be conducted on subjects vaccinated with BNT162b2. A variety of subgroup analyses are planned, along with multiple sensitivity analyses that will test how variations in study design affect results.

Primary Objectives:

Aim 1: Describe profiles, vaccine utilization and resource use among subjects with IC conditions vaccinated with BNT162b2

Aim 2: Evaluate incidence rates of breakthrough infections among subjects with IC conditions fully vaccinated with BNT162b2

Aim 3: Evaluate the clinical presentation of vaccine breakthrough cases among subjects with IC conditions, including time to infection and severity of disease (hospitalization, mortality)

Secondary Objectives

Evaluate Aims 1, 2, 3 and HCRU/costs over time and stratified by relevant patient characteristics (eg, age), in specific IC conditions and by vaccination type (eg, any Mrna).

Exploratory Objective

Generate early estimates of the effectiveness of BNT162b2 in preventing COVID-19 infection, stratified by relevant patient characteristics (eg, age), in specific IC conditions.

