Intensive Care Unit (ICU)	Outcome	HealthVerity Vaccine Data	A claim with a procedure code indicative of ICU utilization during a hospitalization that occurs after the breakthrough COVID-19 diagnosis or at the same time/episode of care 1 st admission and readmissions will be differentiated.
Invasive Mechanical Ventilation (IMV) / Extracorporeal Membrane Oxygenation (ECMO)	Outcome	HealthVerity Vaccine Data	A claim with a procedure code indicative of IMV/ECMO utilization during a hospitalization that occurs after the breakthrough COVID-19 diagnosis or at the same time/episode of care Includes both 1 st admission and readmissions.
Inpatient Death	Outcome	HealthVerity Vaccine Data	Death that occurs on or after the date of the breakthrough COVID-19 diagnosis. The date of death will be assumed to be the same as the date of the last recorded encounter in the database.

PFIZER CONFIDENTIAL

Table 5. COVID-19 Healthcare resource use and Costs definitions

Variable	Role	Data source(s)	Operational definition
			
Death information is available from the Charge Description Master (CDM) data and is provided as year-month of death only.
 
Time to death will also be explored.

Length of Stay (LOS)	Outcome	HealthVerity Vaccine Data	
Length of stay (LOS) associated with different types of hospitalization treatments mentioned above (eg, ICU), applicable for first index hospitalization and/or readmissions.

Costs	Outcome	HealthVerity Vaccine Data	
Non-zero costs associated with any of the previously listed Outpatient and Inpatient encounters (but death).
 
Charges may be assessed in sensitivity analyses to interpret the cost data.

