8.7. Data analysis

Data analyses will follow extensive feasibility analyses aimed at determining whether a full study and the assessment of vaccine effectiveness are feasible, as illustrated below:

Study implementation approach

Characteristics of the IC, non-IC and total population (IC + non-IC) groups will be described. Descriptive statistics for continuous variables will include N (number of patients), mean, median, standard deviation, Q1, Q3, minimum, and maximum. Categorical variables will be described using frequency counts and percentages.

The incidence rate of breakthrough cases of SARS-CoV-2 infection will be determined based on the following:

- Among fully vaccinated patients, those who have a claim for COVID-19 (ICD-10-CM: U07.1) that occurs on or after >14 days following their second dose of an mRNA vaccine (or 1st dose of Johnson & Johnson) will be considered to have had a breakthrough event. The time from 14 days after the qualifying dose until the breakthrough event will be the person time at risk.

PFIZER CONFIDENTIAL

- Among fully vaccinated patients with no evidence of COVID-19 after their qualifying dose, the time from 14 days after the qualifying dose until the end of follow-up will be the person time at risk.

[figure not shown]
The incidence rate of breakthrough cases of SARS-CoV-2 infection will be calculated as the number of patients who experience the event divided by the observed time at risk, and reported per 100 person years. Poisson 95% confidence intervals will be reported for the incidence rates.

Absolute effect measures such as risk difference between non-IC and IC will be reported. Time period specific effect estimates (eg, at 6 months after vaccination) may be estimated if feasible. The characteristics of the breakthrough infections will be described, including clinical presentation and severity.

The primary analysis will describe results among the non-IC cohort and the IC cohort who are vaccinated with BNT162b2. Subgroup analyses will include results for clinically meaningful subgroups as defined by vaccination type, relevant patient characteristics (eg, age), and each IC condition as listed below:

- HIV/AIDS
- Solid malignancy
- Bone marrow transplant
- Organ transplant (excluding bone marrow)
- Rheumatologic/inflammatory
- Primary Immunodeficiencies
- Other immune condition
- CKD or ESRD
- Hematologic malignancy

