8.8. Quality control

Data in HealthVerity's COVID Healthcare database are collected weekly in an electronic format. HealthVerity employs its foundational product to match patients between different data sources with high accuracy. However, not all data points are available in every data source and as a result, not all variables in the database are completely populated. In addition, the database contains both pre- and post-adjudicated claims and, based on the data source, adjudication may or may not be captured. To maximize data completeness and uniformity, it may be necessary to exclude certain data sources from the analysis due to differences in data structure and content.

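### The secondary cost outcome keeps only non-zero costs, states no unit or denominator, and comes with no mean cost over all breakthrough cases

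*Combined protocol and SAP*

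**What the plan says.** The last row of Table 5 (section 8.3) defines costs as "Non-zero costs associated with any of the previously listed Outpatient and Inpatient encounters (but death"). The encounters listed above it are ED visits, outpatient hospital visits, other outpatient visits, hospitalization, ICU care and IMV/ECMO. The row gives no unit, denominator, time window or reason for leaving out zeros. The only sensitivity analysis named for costs is optional: "Charges may be assessed in sensitivity analyses to interpret the cost data".

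Costs belong to a secondary objective (section 7): "Evaluate Aims 1, 2, 3 and HCRU/costs over time and stratified by relevant patient characteristics (eg, age), in specific IC conditions". Section 8.7 has no cost-specific method. Its general rules apply: "Descriptive statistics for continuous variables will include N (number of patients), mean, median, standard deviation, Q1, Q3, minimum, and maximum", and "Categorical variables will be described using frequency counts and percentages". It adds that "The primary analysis will describe results among the non-IC cohort and the IC cohort who are vaccinated with BNT162b2".

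Section 8.8 says that the database mixes claims from before and after adjudication and that, depending on the source, "adjudication may or may not be captured".

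**The concern.** A non-zero filter treats two kinds of zero alike. A breakthrough case that never entered hospital has a true inpatient cost of zero, and that zero belongs in a mean per case. A claim with no captured adjudication may carry a zero or blank amount that is really missing, and it does not belong in the mean as zero. Dropping both leaves a mean among users with a recorded amount.

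That figure describes the price of care once used. It does not describe what a breakthrough infection costs. The IC and non-IC cohorts may differ mainly in how often hospital care is needed, and a users-only mean leaves that part out. Readers will compare the two cohorts' costs whether or not a test is planned, and could conclude that costs are similar when cost per case is not.

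**Working it through.** The plan states no cost, hospitalization rate or event count, so there is no figure to reproduce. The check asks what a non-zero mean would show under each possible unit.

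**Assumed inputs (none from the documents).** Hospitalized share of breakthrough cases: p0 = 10% in non-IC; p1 = 10% to 40% in IC. Cost per stay: H = 20,000. Outpatient cost per case: O = 500, from one outpatient encounter. H and O are equal in both cohorts.

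**Identity.** Mean per case = share using × mean among users. For inpatient cost, the per-case ratio is (p1/p0) × (H1/H0), where H1 and H0 are the IC and non-IC costs per stay. The users-only ratio is H1/H0 alone, so any difference in p drops out.

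**Unit A: per setting, users only (inpatient).** With p1 = 30%, users-only means are 20,000 and 20,000, ratio 1.0. Per case they are 0.10 × 20,000 = 2,000 and 0.30 × 20,000 = 6,000, ratio 3.0.

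**Unit B: per encounter, all types pooled.** (O + pH)/(1 + p) gives 2,500/1.10 = 2,273 and 6,500/1.30 = 5,000, ratio 2.2. Total cost per case is 2,500 versus 6,500, ratio 2.6. The contrast is diluted, not hidden. If IC cases instead have 2 to 4 times as many encounters of the same mix, the per-encounter ratio stays 1.0 while the per-case ratio is 2 to 4.

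**Unit C: patient total.** If every case has at least one costed claim, no case is dropped: 2,500 versus 6,500, ratio 2.6, equal to the all-case ratio.

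IC to non-IC ratios over the assumed range of p1:

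| p1 | A: users only, inpatient | Inpatient per case | B: pooled encounters | C: patient total (= total per case) |
|---|---|---|---|---|
| 10% | 1.0 | 1.0 | 1.0 | 1.0 |
| 15% | 1.0 | 1.5 | 1.34 | 1.4 |
| 20% | 1.0 | 2.0 | 1.65 | 1.8 |
| 30% | 1.0 | 3.0 | 2.2 | 2.6 |
| 40% | 1.0 | 4.0 | 2.67 | 3.4 |

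**Unit C with zero recorded amounts.** Let a share q of outpatient-only cases have a recorded total of zero (p1 = 30%). The non-zero mean is [p(H+O) + (1−p)(1−q)O] / [p + (1−p)(1−q)]. The all-case mean, with those zeros kept as zeros, is the numerator alone. At q = 50%, non-IC is 2,275/0.55 = 4,136 and IC is 6,325/0.65 = 9,731, ratio 2.35. The all-case ratio is 6,325/2,275 = 2.78.

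| q | Non-zero ratio | All-case ratio |
|---|---|---|
| 0% | 2.6 | 2.6 |
| 25% | 2.52 | 2.69 |
| 50% | 2.35 | 2.78 |
| 75% | 1.97 | 2.88 |
| 90% | 1.52 | 2.95 |
| 100% | 1.0 | 3.0 |

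**Keeping every zero is not safe either.** Suppose the zeros are missing amounts, unrelated to true cost, in 40% of non-IC and 10% of IC cases. The zeros-in means are 2,500 × 0.6 = 1,500 and 6,500 × 0.9 = 5,850, ratio 3.9 against a true 2.6.

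**The case against.** The strongest reply is that the plan never says means are taken per setting among users. A breakthrough case exists only because of a claim with the COVID-19 diagnosis code (Table 4), and any outpatient claim outside the ED and hospital categories is itself a listed encounter (Table 5). True zero use per patient should therefore be rare, and a patient-total mean keeps the contrast. This stands, and it limits the point to the per-setting and per-encounter readings, plus patient totals where many amounts are recorded as zero.

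Second, use of each setting is a separate outcome reported with counts and percentages, so a reader could multiply share by mean. That works only if the denominators match. An encounter without a recorded amount counts as use but drops out of cost, and the plan does not examine whether such losses are related to cost.

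Third, dropping zeros on unadjudicated claims is a defensible way to handle missing amounts, and section 8.8 allows sources to be excluded. The first half is right, as the 3.9 against 2.6 example shows. The permission in section 8.8 is general, however, and gives no rule for costs.

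Three stronger readings are tempting and not supported:
- A reader might infer that the plan will hide a several-fold cost difference. That depends on the unstated unit and on assumed rates, and the ratio of exactly 1.0 comes from assuming equal cost per stay.
- A reader might infer a tenfold overstatement when 90% of cases are zeros (1/(1 − 0.9) = 10). That can describe one setting such as inpatient care. It fits poorly with total cost, since every case has a claim.
- A reader might infer selection by payer. Section 8.8 ties adjudication to data source, not payer.

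**Conclusion.** The point holds in a limited form. The non-zero restriction is a stated rule, and nothing in the plan supplies a mean over all breakthrough cases or separates non-use from a missing amount. Whether this matters little or a great deal turns on a unit that the plan leaves open. On the per-setting reading it can remove the whole contribution of hospitalization frequency; on the pooled-encounter reading it can dilute it; on the patient-total reading it does little until a large share of outpatient-only cases carry zero amounts. All sizes shown rest on assumed shares and unit costs, and the documents do not allow the actual size to be derived. Costs are secondary and descriptive and no cost test between cohorts is specified, so this affects the interpretation of one secondary outcome and leaves the primary aims untouched.

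**What to change.** In the Costs row of Table 5 and in section 8.7:

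- State the unit, the denominator and the time window for costs.
- Keep the mean among users, beside the proportion using each setting.
- Add mean cost per breakthrough case, in total and by setting, with a bootstrap confidence interval. The denominator is all breakthrough cases in sources with adjudicated amounts, with zero entered for settings not used.
- Treat zero or blank amounts on unadjudicated claims as missing, not as zero, and report their share by cohort and data source.

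The cost is a change of wording, one more table, and a smaller cost sample where sources lack adjudication. Results would then apply to the sources retained, which the report should say.

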8.4. Data sources

The HealthVerity database contains the largest all-payer (commercial, Medicare, and Medicaid) collection of US healthcare administrative data that links patients' journeys across inpatient admissions, outpatient visits, laboratory visits, and pharmacy services, including COVID-19 tests and vaccinations. Electronic medical records, including Veradigm data, are integrated with the administrative claims data from multiple sources to capture a relatively complete summary of patients' clinical history, including comorbid conditions and other risk factors that may predispose individuals to infections and complications, and use of healthcare resources. With monthly updates available, this data source provides a nearly real-time longitudinal view of patients' journeys across multiple sites of care. All data sets contained within the HealthVerity database are secured and encrypted and all patient information is deidentified. Thus, the data source is fully compliant with the Health Insurance Portability and Accountability Act (HIPAA).

8.5. Study size

The sample size for this study is fixed by the duration of the observation window. No formal sample size computation will be performed. All subjects who meet the inclusion/exclusion criteria will be included in the analyses.

Feasibility analyses confirmed the availability of data to identify vaccinated subjects, subjects with underlying IC conditions, and breakthrough infections. The current study is mainly descriptive in nature. For the exploratory aim, the entire source population available in the HealthVerity database will be included in the analysis.

[figure not shown]

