8. RESEARCH METHODS

8.1. Study design

This study will be a retrospective database analysis utilizing data sets within the HealthVerity database (Philadelphia, Pennsylvania) covering the time period 01 December 2018 through 08 July 2021 (or latest data available) to describe the characteristics of subjects with IC conditions vaccinated with BNT162b2 and to evaluate the incidence of SARS-CoV-2 breakthrough infections.

Study period: 01 December 2018 – 08 July 2021 (or latest data available)

Index identification period: 11 December 2020 – 08 July 2021 (or latest data available; inclusive)

Index date: The first record for a SARS-CoV-2 vaccine (primary analysis: BNT162b2; sensitivity analyses: any Mrna, any authorized vaccine) from a medical claim, pharmacy claim, or chargemaster record.

Baseline period: 12-month period prior to the index vaccination date

Follow-up period: Variable period beginning after the index date and continuing until the earliest of the following: end of the study or end of continuous insurance enrollment.

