8.2. Setting

The primary analysis of this study will include all people at least 12 years of age with at least one vaccine claim (primary analysis: BNT162b2; sensitivity analyses: any Mrna, any authorized vaccine) between 11 December 2020 and 08 July 2021 (or latest date available) from the HealthVerity HealthCare Database. Patients included in the study will be required to have 12 months of continuous medical enrollment prior to the receipt of their first vaccine and have no evidence of a SARS-CoV-2 infection in the year prior to being vaccinated.

The study population will be stratified into two cohorts: non-immunocompromised and immunocompromised. Patients with IC conditions will be identified using a modified implementation of an algorithm developed by Greenberg et al – and later modified and

expanded by Patel et al – for administrative claims based on claims and healthcare records identified in the 12 month baseline period.^{24, 25}

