8.2.1. Inclusion criteria

Patients must meet all of the following inclusion criteria to be eligible for inclusion in the study:

1. Unique enrollees in the HealthVerity Vaccine dataset any time **after** 10 December 2020
2. At least 12 years on the index date (ie, first vaccination date)
3. No evidence of prior COVID-19 infection (a medical claim, pharmacy claim, or chargemaster record with an International Classification of Diseases, 10th Revision, Clinical Modification (ICD-10-CM) diagnosis code of U07.1) in the 12 months prior to the index date
4. Have 12 months of continuous enrollment with medical benefits (with or without pharmacy benefits) prior to the index date

Subjects with an IC condition were identified via an algorithm originally developed and validated by Greenberg et al²⁴ for use in administrative claims database studies. For this study, this algorithm will be modified and expanded based on expert medical opinion. The algorithm is depicted in [Figure 1](#).

Subjects will be identified as immunocompromised if they had ≥ 1 hospitalization or ≥ 2 outpatient visits on separate dates with an ICD-10-CM code on a healthcare claim indicating an IC condition or if they had usage of specific immunosuppressive medications during the 12-month baseline period. The IC case definition will incorporate 8 groups based on clinical diagnoses only, 1 group based on both clinical diagnoses and usage of immunosuppressive medication, and 2 other groups based on usage of immunosuppressive medication only, for a total of 11 groups with an IC condition ([Figure 1](#)). Subjects with >1 IC condition will also be assessed, for a total of 12 mutually exclusive groups for inclusion in this study. The list of ICD-10-CM codes used to identify IC cases by diagnosis and list of immunosuppressive medications are shown in the Annex.

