- IS drug use: >14 days IS medications (chemotherapy, immuno-modulators (IM), or corticosteroids excluding low-dose [<60mg/day] prednisone – See Drug List) and not falling into any of the above 9 condition groups
- >14 days of anti-metabolite use and not falling into any of the above 10 condition or drug use groups
- More than 1 IC condition

PFIZER CONFIDENTIAL

Analyses for younger cohorts (eg, 12-15) will also be conducted, as data accumulates.

For the exploratory aim, the Screening Method will be used to calculate VE for the overall study population of subjects with an IC condition and also stratified VE estimates for the different immunocompromised subject groups, with VE also determined for those subjects with >1 IC condition²⁶. We will use the proportion of the population that are vaccinated (PV) and the proportion of subjects with breakthrough SARS-CoV-2 infections that are vaccinated (PCV) to calculate VE using the following formula:

$$VE = (PV - PCV) / [PV(1-PCV)]$$

where PV = the proportion of the population that is vaccinated (ie, vaccination coverage) and PCV = the proportion of subjects with breakthrough SARS-CoV-2 infections that are vaccinated.

Additionally, breakthrough incidence rates and VE will be stratified by age at diagnosis (eg, < 65 and \geq 65 years of age at index vaccination).

Sensitivity analyses will be conducted to test the robustness of findings by varying key study design aspects (eg, continuous enrolment, IC case definition) and data analysis techniques. Other statistical techniques (eg, matched analyses, multiple regression, propensity scores) may be applied on an exploratory basis after careful examination of potential confounders (eg, age, time from vaccination). Exploratory analyses related to alternate dosing may also be conducted upon feasibility results, and as recommendations from public health authorities evolve. The analyses (entirely or in part) will be conducted over time and updated on a rolling basis as monthly data cuts become available.

While the analyses will be focused on the IC population, analyses will also be conducted (in part or entirely) on the non-IC population, the total (IC + non-IC) population or relevant subgroups (eg, other high-risk conditions, vaccination status) to support the interpretation of findings.

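### The population for the screening-method vaccine effectiveness is inconsistent, and its eligibility rules hang on a vaccination date that unvaccinated people do not have

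*Combined protocol and SAP*

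**What the plan says.** Section 8.5 gives a general rule, "All subjects who meet the inclusion/exclusion criteria will be included in the analyses", and then a separate one for VE: "For the exploratory aim, the entire source population available in the HealthVerity database will be included in the analysis". Section 8.7 describes the VE population differently: "the Screening Method will be used to calculate VE for the overall study population of subjects with an IC condition". Under section 8.2 the study population consists of people aged 12 or over with at least one vaccine claim.

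Two criteria in section 8.2.1 matter here. Criterion 3 requires "No evidence of prior COVID-19 infection" (code U07.1) in the 12 months before the index date. Criterion 4 reads: "Have 12 months of continuous enrollment with medical benefits (with or without pharmacy benefits) prior to the index date". Section 8.2 repeats the second in terms of vaccination: "Patients included in the study will be required to have 12 months of continuous medical enrollment prior to the receipt of their first vaccine". Section 8.1 defines the index date as "The first record for a SARS-CoV-2 vaccine", and the baseline period, from which IC status is taken, as the 12 months before it. No substitute date is given for a person who was never vaccinated.

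The VE formula in section 8.7 is followed by "where PV = the proportion of the population that is vaccinated (ie, vaccination coverage". The text does not say which population that is, or whether the section 8.2.1 criteria apply to it or to the cases.

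**The concern.** The screening method compares the odds of vaccination among cases with the odds of vaccination in the population that gave rise to them. It needs vaccinated cases, unvaccinated cases and coverage to come from the same people under the same entry rules. Here the two sections that name the VE population disagree, and the entry rules can be evaluated only for vaccinated people. An analyst must therefore make an unstated choice, and different choices can give different VE.

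The estimates at stake are VE overall and by IC group. The distortions below are larger in absolute terms when VE is lower, and section 6 reports lower VE in IC patients. An artefact of selection could therefore be taken for a real difference between IC and non-IC people.

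**Working it through.** **Nothing to reproduce.** The documents give no PV, PCV, expected VE or sample size. Every input below is an assumption chosen to show the scale.

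**Step 1: the formula.** VE = (PV − PCV) / [PV(1 − PCV)] equals 1 − [PCV/(1 − PCV)] × [(1 − PV)/PV]. The algebra is correct. Any factor that multiplies only the vaccinated cases, only the unvaccinated cases, or only one side of PV passes straight into 1 − VE. The results below therefore do not depend on PV.

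**Step 2: section 8.7 taken literally.** If the study population contains only people with a vaccine claim and vaccinated means at least one dose, PV = 1 and every case is vaccinated. PCV is then also 1 and the formula is 0/0. If vaccinated means fully vaccinated, the comparator becomes people with an incomplete recorded course, not unvaccinated people. Unvaccinated people have to come from the wider source population in section 8.5.

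**Step 3: the rules bind only vaccinated people.** These are alternative scenarios. They need different readings of the plan and must not be added together.

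- *Prior infection excluded only among the vaccinated.* A share s of the unvaccinated was previously infected, with protection p. Observed VE = 1 − (1 − VE)/(1 − s·p).
  - True VE 60%: s = 0.1, p = 0.6 gives 1 − 0.40/0.94 = 57%; s = 0.3, p = 0.8 gives 1 − 0.40/0.76 = 47%.
  - True VE 80%: 1 − 0.20/0.94 = 79%, and 1 − 0.20/0.76 = 74%.
- *Vaccinated cases filtered, PV not filtered.* A share e of vaccinated cases meets section 8.2.1. Observed VE = 1 − (1 − VE)·e.
  - True VE 60%: e = 0.9 gives 1 − 0.40 × 0.9 = 64%; e = 0.7 gives 1 − 0.40 × 0.7 = 72%.
  - True VE 80%: 1 − 0.20 × 0.9 = 82%, and 1 − 0.20 × 0.7 = 86%.
- *Enrolment required only of the vaccinated.* Suppose 20-40% of the unvaccinated are not enrolled and half of their cases are captured.
  - True VE 60%: 1 − 0.40/(0.8 + 0.2 × 0.5) = 56%, and 1 − 0.40/(0.6 + 0.4 × 0.5) = 50%.

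**Step 4: when no bias arises.** If vaccinated people are restricted equally in PV and PCV, and the restriction is unrelated to risk, the factor cancels and the true VE is returned. One eligibility rule for everyone, vaccinated or not, also returns the assumed true values of 60%, 80% and 95% at PV of 0.3, 0.5 and 0.7.

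**Step 5: the rules are waived for everyone.** PV and PCV then share one source, and the mismatch in step 3 disappears. However, IC status is defined only from a 12-month window before vaccination. It remains undefined for the unvaccinated, and it is incompletely observed for anyone with less than 12 months of enrolment. Cases outside enrolment may also be missed. I put no figure on this, because its effect depends on how capture differs between the groups.

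**The case against.** The strongest reply is that the specific sentence in section 8.5 overrides the general one and waives the criteria for all. Cases and coverage would then share one source. That is a fair reading, and no section says otherwise. A reader might infer that vaccinated cases come from the screened cohort while coverage comes from an unscreened one, so that VE is biased. The documents do not support that as a fact. They never say that the criteria bind vaccinated people in the VE analysis, equal restriction cancels, and the direction differs between scenarios. Nor do they say that people with a short look-back are counted as non-IC.

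The upper end of the prior-infection scenario is also generous. It assumes that the U07.1 screen removes every previous infection among the vaccinated, while section 8.9 concedes underreporting in claims.

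Other mitigations count for something. VE is exploratory, the study is mainly descriptive, and section 8.7 makes VE subject to feasibility work, shown in a figure not available here. Section 8.7 also plans sensitivity analyses that vary enrolment and the IC definition, and allows matching, regression or propensity scores.

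What remains is that the waiver reading leaves IC status undefined for unvaccinated people, although IC-specific VE is the planned output. The generic sensitivity analyses are not tied to VE and do not align PV with PCV.

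**Conclusion.** The defect is an inconsistent and incompletely defined VE population, not a demonstrated bias. Sections 8.5 and 8.7 name different populations, one of which contains no people without a vaccine claim, and the entry rules have no anchor for the unvaccinated. Both ways of resolving this are unsatisfactory. Applying the rules only to vaccinated people may bias VE in either direction: under the stated assumptions a true 60% reads about 47-57% in one scenario or 64-72% in another. Waiving them for all leaves IC status and case capture without assurance. The net direction is unknown, and the size rests wholly on assumed inputs. The change should be made before VE is computed. The primary aims are unaffected.

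**What to change.** In sections 8.5 and 8.7, replace the entire-source sentence with one population that supplies both PV and PCV:

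- For each calendar month (or from a matched pseudo-index date), include all persons, vaccinated or not, who at the start of the month are at least 12 years old, have 12 months of prior continuous medical enrolment, and have no U07.1 in the preceding 12 months, as in criterion 3.
- Take IC status from that same 12-month window.
- PV is the vaccinated share of these persons. PCV is the vaccinated share of all first U07.1 cases arising among them during the month while enrolled. Use one definition of vaccinated, read at the same time point, for both.
- Later disenrolment does not remove a case already counted.
- Combine the months in a stratified VE estimate, and keep the entire-source version as a sensitivity analysis.

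Defining PCV over all first cases also avoids a literal problem. Section 8.7 takes PCV among breakthrough infections, which Table 4 limits to fully vaccinated patients, so PCV would be 1.

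The data start on 01 December 2018, so a 12-month look-back is available from the first vaccination month. The cost is a smaller VE population, slightly wider intervals, and extra programming of index dates and look-backs for unvaccinated people.
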